5.13.3.6 Immunological Markers from Blood and Biopsy Samples

This endpoint will not be evaluated within the scope of this SAP.

Listings will detail information for blood and biopsy samples taken for immunological marker assessment.

5.14 Multiplicity

All endpoints and the supportive analyses will be considered as descriptive evidence of efficacy and will be analysed without any procedures to account for multiple comparisons.

5.15 SAFETY EVALUATION

5.15.1 Adverse Events

AEs will be coded using the latest MedDRA dictionary version. The version used will be indicated in the data summaries and listings.

A treatment-emergent adverse event (TEAE) is defined as an AE that started on or after the start of the administration of IMM-101. If adverse event dates are incomplete and it is not clear whether the adverse event was treatment-emergent, it will be assumed to be treatment-emergent.

The relationship with each study treatment will be entered in to the eCRF for IMM-101, nivolumab and ipilimumab. A treatment-related TEAE is defined as a TEAE that is possibly, probably or definitely related to the study treatment. For each treatment, where the TEAE has a missing relationship it is assumed to be related to the treatment for analysis purposes.

A summary table will present the following:

- TEAEs (events and subjects).
- Serious TEAEs (events and subjects).
- Treatment-related TEAEs (relating to IMM-101 and/or nivolumab and/or ipilimumab) (events and subjects).
- Immune-related TEAEs (events and subjects).
- TEAEs with a Common Terminology Criteria for Adverse Events (CTCAE) Grade of 3 or above (events and subjects).
- TEAEs leading to discontinuation of IMM-101 (subjects only).

- TEAEs leading to withdrawal from study (subjects only).
- TEAEs leading to death (subjects only).
- TEAEs by CTCAE grade (1 to 5) (subjects only).
- TEAEs by severity (mild/moderate/severe/life threatening/death) (subjects only).
- TEAEs by relationship to study treatment and the pooled study treatment related category (subjects only).

In the above summaries, if a subject experienced more than one TEAE, the subject will be counted once using the most related event for the “by relationship to study treatment” and “related to IMM-101/nivolumab/ipilimumab” summaries, at the worst grade for the “by CTCAE grade” summary, and at the worst severity for the “by severity” summary.

A summary table will also be produced for Cohort B subjects only for AEs which occur at or after the start of infusion of ipilimumab. Any nivolumab related TEAEs occurring after the start of ipilimumab administration will be included. The summary will present the following:

- TEAEs (events and subjects).
- Serious TEAEs (events and subjects).
- Treatment-related TEAEs (relating to IMM-101 and/or ipilimumab) (events and subjects).
- Immune-related TEAEs (events and subjects).

The following tables will be presented:

- TEAEs by SOC and PT.
- TEAEs by SOC, PT and relationship to IMM-101/nivolumab/ipilimumab and the pooled related categories (related/unrelated).
- Serious TEAEs by SOC and PT.
- Immune-related TEAEs by SOC and PT.
- TEAEs with a CTCAE grade of 3 or above by SOC and PT.

For all of the above, SOC and PT will be presented in decreasing frequency of the total number of subjects with TEAEs.

Further details of the above five tables are given below:

1. If a subject experienced more than one TEAE, the subject will be counted once for each SOC and once for each PT.
2. If a subject experienced more than one TEAE, the subject will be counted once for each PT.
3. If a subject experienced more than one TEAE, the subject will be counted once for each SOC and once for each PT at the worst severity and/or CTCAE grade.
4. If a subject experienced more than one TEAE, the subject will be counted once for each SOC and once for each PT using the most related event.

Adverse event data will be listed in full and this will also include a treatment emergent flag, the time of onset in relation to each treatment and the action taken for each treatment. Separate listings will be provided for serious AEs, immune-related AEs, AEs with a CTCAE grade of 3 or above, AEs leading to study withdrawal or IMM-101 discontinuation and AEs with a fatal outcome.

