- 2. Patient must have a tumour sample (archived tissue in the last 3 months or newly obtained biopsy) that is adequate for PD-L1 assessment prior to enrolment. Patients will be eligible to participate regardless of the level of PD-L1 expression. Patients with an inadequate archived sample may obtain a new biopsy and patients with an inadequate newly obtained biopsy may undergo one further re-biopsy at the discretion of the investigator.

For cohort B, the following inclusion criteria must also be met for a patient to be eligible to participate in this study:

1. Patient is either currently on (or has previously received) treatment with an anti-PD-1 therapy (monotherapy or in combination) for advanced melanoma and has progressive disease by RECIST 1.1 after at least 3 doses of anti-PD-1 given as monotherapy or at least 2 doses of anti-PD-1 given in combination regimes, and has not received any therapy since for advanced melanoma. The last dose of PD-1 targeted therapy must have been received no more than 12 weeks prior to the start of Screening but more than 6 weeks prior to first IMM-101 administration. For all patients in cohort B, progression must have occurred during the PD-1 targeted treatment and the investigator must have deemed it appropriate to continue/start treatment with nivolumab beyond disease progression.

- 2. Patients must have recovered from any AEs related to prior anti-PD-1 containing regime to Grade 1 or have resolved.
- 3. Patients with a BRAF mutation must have taken at least one BRAF- and/or MEK-targeted therapy, unless patients are not candidates for, or have refused, these therapies. Anti-PD-1 therapy must be the current or last treatment for advanced melanoma prior to study entry.

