# 9.2.5 Treatment-Emergent Adverse Events

A treatment emergent adverse event (TEAE) is defined as any event not present prior to the initiation of study treatment or any event already present that worsens in either intensity or frequency following exposure to the treatment.

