## 9.5 ASSESSING AND RECORDING SAFETY PARAMETERS

All AEs will be recorded on the patient's eCRF from the time of informed consent. All AEs will be followed until resolution, death, or 30 days after the last administration of study treatment (whichever comes first). The Investigator may contact the patient by telephone to obtain the information. Related SAEs will be recorded regardless of time from last dose and added to the eCRF if the occurrence is prior to final Investigator sign-off of the eCRF. SAEs will be recorded up to 30 days from the last administration of study treatment. All SAEs will be followed up until resolution or stabilisation.

Injection site reactions will be assessed by type and grade and recorded in the patient's eCRF before each injection of IMM-101. These will only be recorded as an AE if deemed appropriate by the Investigator, but any injection site reactions of Grade  $\geq$ 3 (Section 9.2.4) should be recorded as an AE.

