# 9.7 RECORDING AND REPORTING ADVERSE EVENTS AND INTERCURRENT ILLNESSES

It is the responsibility of the Investigator to document all AEs that occur during the study from patient entry (i.e., informed consent). An AE includes any noxious, pathological or unintended change in anatomical, physiological or metabolic functions as indicated by physical signs, symptoms and/or laboratory changes whether or not associated with the study drug and whether or not considered related to the study drug. This includes an exacerbation of pre-existing conditions or events, intercurrent illnesses or drug interaction. Anticipated day-to-day fluctuations of pre-existing conditions that do not represent a clinically significant exacerbation or worsening need not be considered AEs.

Patient entry into the study is defined as the time at which informed consent is obtained (this must be before any protocol-specific diagnostic procedures or interventions). All AEs that occur after informed consent has been provided must be reported regardless of whether or not they are considered drug related.

Adverse events will be elicited by asking the patient a non-leading question, for example "Have you experienced or are you experiencing any new or changed symptoms since we last asked/since your last visit?" All AEs must be reported on the appropriate page of the patient's eCRF.

All AEs occurring in patients receiving nivolumab or ipilimumab should be reported irrespective of whether they are identified as being expected as per the product labelling or not.

Each AE will be assigned a CTCAE severity/intensity category as described in Section 9.2.4.

If there is a change in severity of an AE, it must be recorded in the patient's eCRF.

Every effort should be made by the Investigator to explain each AE and assess its relationship, if any, to study drug treatment (IMM-101, nivolumab and, if used on study for patients in cohort B, ipilimumab). Causality should be assessed using the categories as described in Section 9.2.3.

The Investigator must report in detail all adverse signs and symptoms following obtaining informed consent which are either volunteered by patients or observed during or following the course of investigational product administration.

Page 71 of 98

In the event of a SAE/SUSAR, the Investigator will also complete the SAE Report form and forward to Bionical-Emas, by email or fax, within 24 hours:

SAE CONTACT DETAILS: Bionical-Emas Ltd.

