### 11.1.3 Safety and Tolerability Endpoints

The primary safety endpoints include the following:

• Incidence, frequency and severity of AEs, Serious AEs, treatment-related AEs (related to IMM-101 and/or nivolumab/ipilimumab (as applicable), immune-related AEs (as listed in the SmPC for nivolumab), Grade 3 and above AEs and AEs leading to IMM-101 discontinuation or study withdrawal throughout the study.

The secondary safety endpoints include the following:

- Incidence and frequency of laboratory parameter abnormalities
- Change from baseline values in laboratory parameter values
- Incidence and frequency of local injection site reactions.

Page 77 of 98

Exploratory safety endpoints include the following:

• For the subgroup of patients in cohort B who receive IMM-101 + ipilimumab as subsequent treatment: The incidence, frequency and severity of adverse events, serious adverse events, treatment-related adverse events and immune-related adverse events (as listed in the SmPC for ipilimumab) experienced following the start of ipilimumab treatment up to the end of the study.

Treatment-emergent AEs (TEAEs) are defined as AEs occurring after the first dose of IMM-101. Only TEAEs will be presented in summary tables and all AEs (i.e., TEAEs and non-TEAEs) will be listed by patient within cohort.

TEAEs will be summarised by MedDRA system organ class and preferred term using standard incidence and frequency tables. The incidence of TEAEs will be presented as the proportion of patients with at least one AE by system organ class and preferred term and frequency of TEAEs will be calculated as the number of events by system organ class and preferred term.

Treatment-related AEs are defined as AEs which are related to study treatment (IMM-101 and/or nivolumab, and/or ipilimumab if after ipilimumab dosing in cohort B). Related AEs will be those assigned by the investigator as definitely, probably or possibly related to study treatment or with an unknown relationship. Relatedness will be assessed to each of IMM-101, nivolumab and ipilimumab separately as well as for the combined treatment combination. The incidence and frequency of treatment-related AEs, SAEs, and immune-related AEs will be presented, as for all TEAEs.

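### Protocol 9.2.5 counts a worsened pre-existing event as treatment-emergent, but Protocol 11.1.3 and SAP 5.15.1 do not, so a Screening AE that worsens on treatment may be left out of the summary tables

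*SAP*

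**What the plan says.** The documents define a TEAE in three places.

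- Protocol 9.2.5 counts events that are new since study treatment began and also "any event already present that worsens in either intensity or frequency following exposure to the treatment".
- Protocol 11.1.3, in the statistics chapter: "Treatment-emergent AEs (TEAEs) are defined as AEs occurring after the first dose of IMM-101". It has no worsening clause.
- SAP 5.15.1: a TEAE "is defined as an AE that started on or after the start of the administration of IMM-101". It has no worsening clause and works from the start date.

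Protocol 11.1.3 then decides what is tabulated: "Only TEAEs will be presented in summary tables and all AEs (i.e., TEAEs and non-TEAEs) will be listed by patient within cohort". The AE tables in SAP 5.15.1 are likewise tables of TEAEs: overall, serious, treatment-related, immune-related, Grade 3 and above, and those leading to IMM-101 discontinuation, withdrawal or death.

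On data capture, Protocol 9.5 states: "All AEs will be recorded on the patient's eCRF from the time of informed consent". Protocol 9.7 adds: "If there is a change in severity of an AE, it must be recorded in the patient's eCRF". The same section treats an exacerbation of a pre-existing condition or event as an AE.

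SAP section 6 lists five changes or clarifications relative to the protocol. None concerns the TEAE definition.

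**The concern.** The primary safety endpoint is the incidence, frequency and severity of AEs on IMM-101 plus nivolumab, and the stated aim is to compare it with published nivolumab data. Those rates come from the TEAE tables. A definition based on start date alone can leave out an event that was mild at Screening and became severe on treatment, which is the kind of change a safety table should show. Except for AEs with incomplete dates, which default to treatment-emergent, the narrower definition can only give the same count as Protocol 9.2.5 or a lower one. Any error therefore runs towards under-reporting.

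The definitions also leave room for inconsistency between sites. If one site logs worsening as a grade change and another opens a new AE, the same clinical course is tabulated at one and not at the other.

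**Working it through.** The plan gives no figure to reproduce. The check compares the definitions, then works out the scale of one affected patient.

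**1. Can an AE have a start date before the first dose?** Yes. AEs are recorded from informed consent (Protocol 9.5, 9.7) and Screening lasts up to 21 days (Protocol 5.1).

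**2. How is a worsening of such an AE classified?** Take an AE that starts at Grade 1 during Screening, is ongoing at first dose, and reaches Grade 3 on treatment.

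| Definition | Worsening entered as a grade change on the existing record | Worsening entered as a new AE with its own start date |
|---|---|---|
| Protocol 9.2.5 | TEAE | TEAE |
| Protocol 11.1.3 | Unclear: the event began before dosing, and worsening is not mentioned | TEAE |
| SAP 5.15.1 | Not a TEAE: start date is before dosing | TEAE |

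**3. Which column applies?** Protocol 9.7 requires a severity change to be recorded but does not say on which record or under which start date. The same section makes an exacerbation an AE, which would support a new entry. The documents do not settle it.

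**4. Does another rule rescue the event?** SAP 5.15.1 treats an AE as treatment-emergent when incomplete dates leave its timing unclear. That does not help here, because the start date is known and falls before dosing.

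**5. What is lost in the first column under the SAP?** The event is absent from the overall TEAE table, from the Grade 3 and above table and, where it qualifies, from the serious, immune-related and treatment-related tables. It remains in the full AE listing, which carries a treatment-emergent flag, and in the separate serious, immune-related and Grade 3 and above listings.

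**6. Scale.** Planned sizes are 18 (cohort A) and 8 (cohort B), from Protocol 11.2 and SAP section 3. For one patient with no other event in the category, the change in incidence is 1/n:

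- cohort A: 1/18 = 5.6 percentage points
- cohort B: 1/8 = 12.5 percentage points
- overall: 1/(18 + 8) = 1/26 = 3.8 percentage points

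These are per-patient weights. The documents give no basis for an expected number of such patients.

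**The case against.** The strongest reply is that the text may already cover the case. Since Protocol 9.7 makes an exacerbation an AE, a site that follows it by opening a new record gives the event an on-treatment start date, and the SAP then counts it. This stands to the extent that the loss is conditional. It does not remove the problem, because no rule requires that method.

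A reader might infer that such events disappear from every safety table. The documents do not support that. It would require the severity change to stay on the existing record, which Protocol 9.7 does not say.

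A reader might also infer that cohort B is the group most exposed, because its entry criterion reads: "Patients must have recovered from any AEs related to prior anti-PD-1 containing regime to Grade 1 or have resolved". But toxicity already present at consent would plausibly be entered as medical history, which under Protocol 8.4.1 covers all active conditions. There would then be no pre-dose AE record, and later worsening would probably be a new AE. The exposed events are mainly those that begin between consent and first dose.

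Nor is this simply the SAP against the protocol: the SAP follows the protocol's own statistics section, and the conflict lies between Protocol 9.2.5 and 11.1.3.

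Finally, the study is small and descriptive, all AEs are listed, and safety data are reviewed every six months, so a careful reader could find these events. That is fair and limits the harm. Listings do not, however, supply the incidence rates that form the primary safety endpoint and are to be set against published data.

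**Conclusion.** The inconsistency is real and affects the definition behind a primary endpoint. Protocol 9.2.5 includes worsening, Protocol 11.1.3 and SAP 5.15.1 do not, the summary tables are limited to TEAEs, and SAP section 6 is silent, so a reader of the SAP cannot tell that 9.2.5 was set aside.

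The consequence is conditional. An AE that begins before the first dose and worsens on treatment is left out of the tables only if the worsening is recorded as a grade change on the existing record. The documents leave that open, and the number of patients affected is unknown. One such patient with no other event in the category would lower an incidence by 5.6 points in cohort A, 12.5 in cohort B or 3.8 overall, assuming planned enrolment is reached.

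A larger figure, 1/5 = 20 points, might be inferred from the five cohort B patients in the interim response review. Under SAP section 4 the interim safety review takes in everyone enrolled by then, so that figure applies only if no further cohort B patients have joined. A demonstrated understatement of toxicity cannot be claimed. What can be claimed is a gap that allows under-counting and inconsistent counting.

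**What to change.** - In SAP 5.15.1 and Protocol 11.1.3, adopt the Protocol 9.2.5 definition: onset on or after the first IMM-101 administration, or present before it and increased in CTCAE grade or frequency afterwards. Tabulate the event at its on-treatment grade and count it once.
- State one recording rule. Post-dose worsening is either entered as a new AE with its own start date or derived from the recorded grade change, but not both, since using both would count the event twice. A rise in frequency cannot be read from severity changes, so if the derivation route is chosen, say how frequency will be captured.
- Record the change in SAP section 6.

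The cost is a wording change in two documents and one extra derivation. Reported AE rates may rise slightly.

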# 9.2.2 Adverse Drug Reaction

During early development studies when clinical experience with a new investigational product or its new usages is limited all noxious and unintended responses to an investigational product related to any dose should be considered adverse drug reactions (ADRs). The phrase "responses to an investigational product" means that a causal relationship between an investigational product and an AE is at least a reasonable possibility, i.e., the relationship cannot be ruled out.

Note that nivolumab and ipilimumab are considered non-investigational medicinal products for this study, used as background SOC for advanced melanoma. Only IMM-101 is considered as the investigational product for this study. Causality of adverse events to IMM-101 as well as to nivolumab and (where used) to ipilimumab will be recorded.

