# 9.2.3 Relationship of Adverse Events

Assessment of causality of AEs to the study drug (IMM-101) and also to nivolumab and to ipilimumab (where used in cohort B) is according to the following guidelines:

Definitely Related – There is clear evidence to suggest a causal relationship, and other possible contributing factors can be ruled out. The clinical event, including an abnormal laboratory test result, occurs in a plausible time relationship to drug administration and cannot be explained by concurrent disease or other drugs or chemicals. The response to withdrawal of the drug (dechallenge) should be clinically plausible. The event must be pharmacologically or phenomenologically definitive, with use of a satisfactory rechallenge procedure if necessary.

Probably Related – There is evidence to suggest a causal relationship, and the influence of other factors is unlikely. The clinical event, including an abnormal laboratory test result, occurs within a reasonable time after administration of the drug, is unlikely to be attributed to concurrent disease or other drugs or chemicals, and follows a clinically reasonable response on withdrawal (dechallenge). Rechallenge information is not required to fulfil this definition.

Possibly Related – There is some evidence to suggest a causal relationship (e.g., the event occurred within a reasonable time after administration of the trial medication). However, other factors may have contributed to the event (e.g., the participant's clinical condition, other concomitant events). Although an AE may rate only as "possibly related" soon after discovery, it can be flagged as requiring more information and later be upgraded to "probably related" or "definitely related," as appropriate.

Not Related – The AE is completely independent of study drug administration, and/or evidence exists that the event is definitely related to another etiology.

Note: Even if the Investigator feels there was no relationship to the study drug, the AE is to be reported.

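### SAP 5.15.1 counts a missing causality entry as related without requiring that the drug was given; if the ipilimumab field is left blank where unused, every TEAE without prior ipilimumab would count as treatment-related

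*SAP*

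**What the plan says.** **SAP 5.15.1.** Three statements matter.

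- Data entry: "The relationship with each study treatment will be entered in to the eCRF for IMM-101, nivolumab and ipilimumab".
- Missing entries: "For each treatment, where the TEAE has a missing relationship it is assumed to be related to the treatment for analysis purposes".
- The summary row that pools the drugs: "Treatment-related TEAEs (relating to IMM-101 and/or nivolumab and/or ipilimumab) (events and subjects".

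The same section plans a table by SOC, PT and relationship to each drug, with pooled related and unrelated categories. SAP 5.4 presents adverse events by cohort and overall.

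**Protocol, collection of causality.** Section 9.2.2: "Causality of adverse events to IMM-101 as well as to nivolumab and (where used) to ipilimumab will be recorded". Section 9.2.3 says that assessment "to ipilimumab (where used in cohort B) is according to the following guidelines", and gives four levels: definitely, probably, possibly and not related. Section 9.7 asks the investigator to assess the relationship to "IMM-101, nivolumab and, if used on study for patients in cohort B, ipilimumab".

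**Protocol, definition for analysis.** Section 11.1.3 defines treatment-related as related to "IMM-101 and/or nivolumab, and/or ipilimumab if after ipilimumab dosing in cohort B". Within that definition it also counts an unknown relationship as related.

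**SAP section 6**, which lists changes from the protocol's planned analysis, has five items. None concerns relatedness.

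**The concern.** Treating a missing causality entry as related is a normal conservative rule when the patient was exposed to the drug. It is not conservative, only wrong, when the patient never received it. The SAP rule runs drug by drug and has no exposure condition, so it does not separate a missing assessment from one that does not apply. Because the pooled category is a union over three drugs, one imputed ipilimumab entry is enough to make an event treatment-related.

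On study, only Cohort B patients can receive ipilimumab. The open fields would be those for all of Cohort A (18 planned patients), for Cohort B patients (8 planned) who never switch, and for Cohort B events before the switch.

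Treatment-related AEs are a component of the primary safety endpoint (SAP 2.2.1), and the AE profile is to be compared with published data on nivolumab alone (SAP 2.1). If the rule took effect, the pooled related row for Cohort A would equal the all-TEAE row and say nothing about causality. The table by relationship would also attribute events to a drug not given.

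**Working it through.** The documents give no figure on this point, so there is none to reproduce. The check traces the rule.

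**Step 1. One event.** Take a Cohort A TEAE that the investigator judged not related to IMM-101 and not related to nivolumab. Pooled related = related to IMM-101 OR nivolumab OR ipilimumab. The first two terms are false, so the result depends on the ipilimumab field.

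| Ipilimumab field | SAP 5.15.1 read literally | Protocol 11.1.3 |
|---|---|---|
| blank | imputed related, so pooled related | not related |
| coded not applicable | not related | not related |
| coded not related | not related | not related |

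The two definitions disagree only in the first row. The protocol's limit, "and/or ipilimumab if after ipilimumab dosing in cohort B", gives the same answer whatever the field holds.

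**Step 2. Which state is likely?** Protocol 9.2.2, 9.2.3 and 9.7 ask for an ipilimumab assessment only where the drug was used, and the scale in 9.2.3 has no not-applicable level. That points towards a blank. Against this, the SAP says that a relationship is entered for all three drugs, and Protocol 11.1.3 mentions an unknown relationship, which is outside the four levels; the eCRF may therefore hold further codes. Neither document shows the coding.

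**Step 3. Size for event counts.** Let *r* be the share of the affected TEAEs truly judged related to a drug the patient had received. Let *b* be the share of the remaining TEAEs whose ipilimumab field is blank.

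- Reported related share = *r* + (1 − *r*)*b*
- Inflation factor = [*r* + (1 − *r*)*b*] / *r*
- All blank (*b* = 1): reported share = 100%, factor = 1/*r*
- None blank (*b* = 0): factor = 1, no effect

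The documents give neither *r* nor *b*. As an illustration only, with *r* assumed between 20% and 70% and *b* = 1, the factor runs from 1/0.2 = 5.0 to 1/0.7 = 1.43.

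**Step 4. Size for subject counts.** SAP 5.15.1 counts a subject once, at the most related event. A subject with at least one genuinely related TEAE is already counted and does not change. With all fields blank, the factor is 1/*s*, where *s* is the share of subjects with any TEAE who have at least one related TEAE. As *s* is usually larger than *r*, the inflation is usually smaller.

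**Step 5. What is untouched.** Relatedness to IMM-101 and to nivolumab is presented separately and does not use the ipilimumab field. Cohort B events after the switch have ipilimumab causality assessed, so a recorded entry stands. A true gap there is a proper use of the rule.

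**The case against.** A reader might infer that every Cohort A TEAE will be reported as ipilimumab-related. The documents do not support that as a certainty. It needs the field to be blank and the blank to be read as missing, and neither is shown. The SAP sentence on data entry can be read as promising an entry for all three drugs. If unused ipilimumab is coded as not related or not applicable, the effect is zero. This stands, and the point is therefore conditional.

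It can also be said that the SAP is based on protocol Version 2.0 and that an unlisted departure was probably not intended, so the limit in Protocol 11.1.3 still governs. That may well be the intention. But SAP 5.15.1 gives its own definition of a treatment-related TEAE, and a programmer working from it would find no exposure condition.

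The imputation itself is not new: the protocol already counts an unknown relationship as related. Only its reach to a drug not given is at issue.

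A reader might also infer a fixed multiple for the overstatement. The range shown above rests on an assumed related share that no document supports, and it applies to event counts only.

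Finally, the study is descriptive, with no hypothesis test, and the AE listings show onset relative to each treatment, so a false attribution could be spotted. That limits the harm but does not correct the summary tables.

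**Conclusion.** The point holds as a defect in the SAP's wording, not as a demonstrated misclassification. SAP 5.15.1 keeps the missing-as-related rule but omits the protocol's limit on when ipilimumab counts, and section 6 does not declare the change.

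If the ipilimumab field is left blank where the drug was not given, the rule read literally makes all Cohort A TEAEs, and all Cohort B TEAEs before or without ipilimumab, treatment-related in the pooled row of the primary safety endpoint. The size is unknown: it ranges from no effect, if the eCRF codes the field, to a reported related share of 100% of those events, if it does not. Mixed practice between sites would give partial inflation, which is harder to notice. The change is worth making before the tables are programmed, because it costs little and does no harm if the eCRF already handles the case.

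**What to change.** In SAP 5.15.1, restate the limit from Protocol 11.1.3 and add an exposure condition to the missing-data rule. For example:

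> Relationship to ipilimumab counts only for TEAEs in Cohort B with onset after ipilimumab dosing has begun. A missing relationship is taken as related only for a treatment that the subject had received on or before TEAE onset. For any other treatment it is not applicable and does not contribute to the pooled related category.

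The rule stays as it is for IMM-101 and nivolumab once given. Check how the eCRF codes ipilimumab causality in unexposed patients, and state this in the SAP. If the sponsor does intend to drop the protocol's limit, section 6 should say so and give the reason.

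The cost is a short addition to the SAP and one date condition in the program. No new data are needed, because the AE listing already requires time of onset relative to each treatment.
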